7.2.2. Fatigue

Evaluate for other possible causes of fatigue (eg anemia, insomnia, depression, hypothyroidism).

Supportive care to cope with fatigue (e.g. strategies to conserve energy, scheduled nap, and exercise).

If not controlled with supportive care, interrupt olaparib treatment; when symptoms are grade 1, restart olaparib treatment per protocol.

7.2.3. Dysgeusia

Supportive care to cope with dysgeusia (appropriate expectation counseling, modification food preparation).

If not controlled with supportive care, interrupt olaparib treatment; when symptoms are grade 1, restart olaparib per protocol.

7.2.4. Diarrhea

Evaluate for other possible causes (eg infection, dietary, concomitant medications). If other sources are ruled out, initiate anti-motility agents for mild to moderate symptoms.

If not controlled with medication, interrupt olaparib treatment; when symptoms are grade 1, restart olaparib treatment per protocol.

7.2.5. Constipation

Evaluate for other possible causes (eg bowel obstruction, dietary, concomitant medications).

If other sources are ruled out, initiate stool softeners and/or laxatives for mild to moderate symptoms.

If not controlled with medication, interrupt olaparib treatment; when symptoms are grade 1, restart olaparib treatment per protocol.

7.2.6. Pneumonitis

Interrupt olaparib and investigate patients with new or worsening respiratory symptoms, such as dyspnea, cough and fever, or a radiological abnormality consistent with pneumonitis.

If pneumonitis confirmed, discontinue olaparib and treat appropriately (glucocorticoids).

7.2.7. Renal Impairment

CrCl 51 to 80 mL/minute: No dosage adjustment necessary; monitor closely for toxicity, as an increase in mean AUC has been observed in patients with mild impairment.

CrCl 31 to 50 mL/minute: Reduce dose to 200 mg twice daily.

 $CrCl \leq 30 \text{ mL/minute}$: There are no dosage adjustments provided in the manufacturer's labeling (has not been studied).

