Inclusion Criteria	 Patient has platinum-sensitive, recurrent ovarian, fallopian-tube or peritoneal cancer. Platinum sensitivity is defined as complete clinical remission after frontline chemotherapy lasting greater than 6 months Patient has completed at least 2 courses of platinum-based chemotherapy and in the most recent course of platinum therapy obtained a PR or CR as defined by the Response Evaluation Criteria in Solid Tumors (RECIST) v1.1 or a CA-125 response, according to Gynecological Cancer InterGroup (GCIG) criteria. BRCA testing required (results not needed for registration) Age ≥18 years old. ECOG performance status score of 0, 1, or 2. See Appendix A Life expectancy greater than 6 months. Normal organ and marrow function as defined below: Absolute neutrophil count (ANC) ≥ 1.5 x 10 /L Platelets ≥ 100 x 10 /L Hemoglobin (Hgb) ≥ 8 g/dL (blood transfusions to reach this amount are allowed) Serum creatinine ≤ 1.5 mg/dL Total serum bilirubin ≤ 1.5 x ULN (in patients with known Gilbert Syndrome, a total bilirubin ≤ 3.0 x ULN, with direct bilirubin ≤ 1.5 x ULN Able to take oral medication. Not pregnant and not breastfeeding. Able to understand and willingness to sign a written informed consent
Exclusion Criteria	 document. Patient has had a prior invasive malignancy diagnosed within the last five years (except [1] non-melanoma skin cancer or [2] prior in situ carcinoma of the cervix or breast [3] has been without evidence of invasive disease for greater than 3 years) Patients receiving any other investigational agents History of allergic reactions attributed to compounds of similar chemical or biologic composition to olaparib Uncontrolled intercurrent illness that could affect their participation in the study including, but not limited to, ongoing or active infection; symptomatic congestive heart failure; unstable angina pectoris; cardiac arrhythmia; known inadequately controlled hypertension; significant pulmonary disease including dyspnea at rest, patients requiring supplemental oxygen, or poor pulmonary reserve; or psychiatric illness/social situations that would limit compliance with study requirements Impairment of gastrointestinal function or disease that may significantly alter the absorption of olaparib Patients who have received prior treatment with a PARP inhibitor History of non-compliance to medical regimens

Study	
Product(s),	Olaparib will be dosed at 300 mg orally twice a day. Twenty-eight days of

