6.1. Agent Administration

Olaparib treatment will be started when CA125 rises by two-fold of their nadir value. Olaparib will be dosed at 300 mg orally twice a day. Twenty-eight days of treatment will be considered one cycle. Patients will be required to maintain a medication diary (See Appendix B).

Patients starting olaparib will continue treatment until disease progression, per RECIST v1.1³⁹ or intolerable toxicity, defined as any grade 3 or 4 adverse event, per National Cancer Institute's Common Terminology Criteria for Adverse Events (CTCAE) v5.0 or Patient Reported Outcomes-Common Terminology Criteria for Adverse Events (PRO-CTCAE), that does not resolve completely or to grade 1 within 28 days after onset. Patients removed from study for unacceptable adverse event(s) will be followed closely until resolution or stabilization of the adverse event (at least 30 days).

Olaparib is FDA-approved for maintenance therapy for patients with platinum sensitive recurrent epithelial ovarian cancer with a complete or partial response to most recent platinum based chemotherapy. Therefore, drug will be covered by standard insurance. Additionally, after discussion with The UPMC Health Plan, they will approve treatment after 2 prior lines even with the delay in standard start time defined by the maintenance indication.

Treatment will be administered on an outpatient basis. Appropriate dose modifications are described in Section 7. No other investigational or commercial agents or therapies may be administered with the intent to treat the patient's malignancy.

Reported adverse events and potential risks are described in Section 7.

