7.2.8. Hepatic Impairment

Child-Pugh classification A or B: No dose adjustment.

Child-Pugh classification C: Use not recommended for use as safety and pharmacokinetics have not been studied in these patients.

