8.1. Adverse Events and Potential Risks List for Olaparib

>10%:

Cardiovascular: peripheral edema (14%)

Central nervous system: fatigue (≤67%), headache (15% to 26%), dizziness (7% to 20%)

Endocrine & metabolic: hypomagnesemia (5% to 14%)

Gastrointestinal: nausea (58% to 77%), abdominal pain (45%), vomiting (30% to 43%), diarrhea (21% to 37%), constipation (16% to 28%), dysgeusia (9% to 27%), dyspepsia (8% to 25%), decreased appetite (16% to 22%), stomatitis (4% to 20%; grades 3/4: 1%)

Genitourinary: urinary tract infection (13% to 14%)

Hematologic & oncologic: increased MCV (57% to 89%), decrease in absolute neutrophil count (25% to 51%; grades 3/4: 7% to 11%), anemia (23% to 44%; grades 3/4: 7% to 21%), neutropenia (5% to 27%; grades 3/4: 6% to 9%), leukopenia (2% to 25%; grades 3/4: 3% to 5%), thrombocytopenia (4% to 14%; grades 3/4: 1%)

Infection: influenza ($\leq 36\%$)

Neuromuscular & skeletal: asthenia ($\leq 66\%$), arthralgia ($\leq 30\%$), myalgia ($\leq 30\%$), musculoskeletal pain ($\leq 21\%$), back pain (14%)

Renal: increased serum creatinine (3% to 45%)

Respiratory: nasopharyngitis (\leq 36%), respiratory tract infection (\leq 36%), rhinitis (\leq 36%), sinusitis (\leq 36%), bronchitis (\leq 28%), cough (16% to 18%), dyspnea (13% to 15%)

1% to 10%:

Cardiovascular: edema (8% to 9%), pulmonary embolism (\leq 1%), venous thrombosis (\leq 1%)

Central nervous system: peripheral neuropathy (5%), depression, insomnia

Dermatologic: skin rash (5% to 6%), dermatitis (1%)

Gastrointestinal: upper abdominal pain (7%)

Hematologic & oncologic: lymphocytopenia (1% to 8%), myelodysplastic syndrome (acute myeloid leukemia; 1%)

Hypersensitivity: hypersensitivity reaction (2%)

Miscellaneous: fever (8% to 10%)

<1%, postmarketing, and/or case reports: pneumonitis

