11. STUDY CALENDAR

Baseline evaluations are to be conducted within 14 days prior to start of trial. Imaging CT scans and x-rays must be done ≤ 4 weeks prior to the start of therapy.

Procedure/Test	Pre- Study	Surveillance every 4 weeks	Day 1 of each cycle	Every 12 weeks	30 day follow- up*	Every 3 months
Informed consent	Х					
Demographics	Х					
Concurrent medications	Х	Х	Х		Х	
Medical history	Х					
Physical exam ^A	Х	Х	Х		Х	
Vital signs ^A	Х	Х	Х		Х	
Height and Weight ^A	Х	Х	Х		Х	
Performance status ^A	Х	Х	Х		Х	
CBC w/diff, platelets A	Х		Х		Х	
Serum chemistry A,B	Х		Х		Х	
CA125 ^A	Х	Х	Х		Х	
PTT/PT/INR ^C	Х					
EKG ^C	Х					
Tumor Measurements D	Х			Х		
Baseline signs & symptoms	Х					
Adverse event evaluation ^E	Х	Х	Х		Х	
Worry and Distress Measures ^F	Х	Х	Х		Х	
Quality of Life and Physical Function Measures ^G	Х			Х	Х	
Financial Toxicity Measures ^H	Х			Х	Х	
Urine or serum B-HCG for WOCBP ¹	X					
Tissue Collection ^J	Х				Х	
PK plasma sample ^K			ХК			

BRCA testing ^L	X			
Survival Follow-up ^M				Х

*Patients should be seen 30 days after completion of treatment to assess for resolution of toxicity

- A. These procedures do not need to be repeated in cycle 1 if done pre-study within 7 days prior to start of protocol therapy.
- B. Albumin, alkaline phosphatase, total bilirubin, direct bilirubin, bicarbonate, BUN, calcium, chloride, creatinine, glucose, potassium, total protein, SGOT [AST], SGPT [ALT], sodium, magnesium, phosphorus
- C. Required pre-study, then as clinically indicated
- D. Prior to olaparib initiation, imaging will only be done for doubling of nadir CA125 or per physician discretion for patient symptoms. Following initiation of olaparib, CT scans will be obtained every 12 weeks as part of surveillance. CT scans can be obtained for rising CA125 or physician preference for patient symptoms before scheduled routine surveillance.
- E. Adverse event evaluation will include both the CTCAE and the PRO-CTCAE (See Appendix D).
- F. Worry and distress measured via Assessment of Survivor Concerns (ASC) (See Appendix E) worry subscale and Impact of Event Scale (IES-R) (See Appendix F).
- G. Health-related quality of life will be measured via The Functional Assessment of Cancer Therapy + Ovarian-specific scale (FACT-O) (See Appendix G) and physical function assessed through the PROMIS Physical Function-20a assesses self-reported performance of physical activities (See Appendix H).

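### Section 7.2.7 gives no instruction at CrCl ≤ 30 mL/min, a range that the creatinine-only entry criterion can admit

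*Combined protocol and SAP*

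**What the plan says.** The only renal entry criterion is "Serum creatinine ≤ 1.5 mg/dL" (synopsis; same limit in 3.1.7). There is no CrCl criterion, no upper age limit and no weight limit, and no exclusion in 3.2 names renal function.

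Section 6.1 states "Olaparib will be dosed at 300 mg orally twice a day" and refers to Section 7 for dose modifications. Drug does not begin at enrollment: "Olaparib treatment will be started when CA125 rises by two-fold of their nadir value".

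Section 7.2.7 works in CrCl. At 51 to 80 mL/min the dose is unchanged, with close monitoring. At 31 to 50 it is cut to 200 mg twice daily. At 30 or below the text reads "There are no dosage adjustments provided in the manufacturer's labeling (has not been studied" and stops there. Section 7.2.8 deals with the corresponding hepatic group, Child-Pugh C, differently: "Use not recommended for use as safety and pharmacokinetics have not been studied in these patients".

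The study calendar (Section 11) marks serum chemistry pre-study and on day 1 of each cycle, but not at surveillance visits. Weight is marked at all three. Note A adds: "These procedures do not need to be repeated in cycle 1 if done pre-study within 7 days prior to start of protocol therapy".

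**The concern.** Entry is screened on one quantity (creatinine) and dosing is governed by another (CrCl), which also depends on age and weight. If creatinine ≤ 1.5 mg/dL can coexist with CrCl ≤ 30, a woman can meet every written criterion and reach the start of olaparib in a range the protocol itself describes as unstudied, with no instruction attached.

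Read literally, the dosing rule also runs the wrong way: moderate impairment requires a reduction, while worse impairment has none stated. The issue is patient safety. Section 7.2.7 itself notes higher mean exposure even in mild impairment, and 8.1 lists grade 3/4 anemia in 7% to 21%.

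**Working it through.** The plan states no figure to reproduce. The check is whether the entry criterion and CrCl ≤ 30 can hold together, and what the protocol then says.

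**Inputs.** Creatinine limit 1.5 mg/dL (synopsis, 3.1.7); CrCl cut-off 30 mL/min (7.2.7); women; no age or weight bound. Assumed: Cockcroft-Gault with actual body weight.

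**Formula.** CrCl = 0.85 × (140 − age) × weight / (72 × creatinine). The highest weight giving CrCl ≤ 30 is therefore 30 × 72 × creatinine / (0.85 × (140 − age)).

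For example, at 1.5 mg/dL and age 75: 3240 / (0.85 × 65) = 3240 / 55.25 = 58.6 kg.

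| Creatinine (mg/dL) | Age 65 | Age 70 | Age 75 | Age 80 |
|---|---|---|---|---|
| 1.5 | 50.8 kg | 54.5 kg | 58.6 kg | 63.5 kg |
| 1.4 | 47.4 kg | 50.8 kg | 54.7 kg | 59.3 kg |
| 1.3 | 44.0 kg | 47.2 kg | 50.8 kg | 55.1 kg |
| 1.0 | 33.9 kg | 36.3 kg | 39.1 kg | 42.4 kg |

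The range is reachable, mainly when creatinine is near the limit.

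**Individual cases at 1.5 mg/dL.**
- Inside: age 65, 50 kg: 29.5; age 75, 55 kg: 28.1; age 80, 60 kg: 28.3.
- Outside: age 75, 60 kg: 30.7; age 65, 60 kg: 35.4; age 60, 70 kg: 44.1.

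**At the start of olaparib.** A patient at CrCl ≤ 30 has no dose tied to her renal function. The other reduced doses belong to other conditions: 250 and 200 mg to toxicity, 150 and 100 mg to CYP3A inhibitors, 200 mg to CrCl 31 to 50. What remains is 300 mg twice daily.

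**After the start.** The creatinine at which CrCl reaches 30 is 0.85 × (140 − age) × weight / (72 × 30).
- Age 80, 60 kg: 3060 / 2160 = 1.417. From 1.3 (CrCl 32.7), a rise of 9%.
- Age 75, 60 kg: 3315 / 2160 = 1.535. From 1.2 (CrCl 38.4), a rise of 28%.
- Age 60, 70 kg: 4760 / 2160 = 2.204. From 1.0 (CrCl 66.1), a rise of 120%.

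The first two women start in the 31 to 50 band, so 7.2.7 already has them on 200 mg twice daily; they would cross 30 at that dose, not at 300 mg. The third would pass through the 200 mg band first, unless the whole fall came between two day 1 chemistries.

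**The case against.** The best defense is that Section 7 does warn the physician. Section 6.1 makes the dose subject to it, and a range with no labeled dose and no data reads as a caution, not as permission. The investigator or a designee reviews all baseline results before enrollment (Section 3), 3.2.4 excludes uncontrolled intercurrent illness, and 6.3 and 6.5 allow treatment to be stopped on judgment. This stands to the extent that nothing obliges anyone to give 300 mg twice daily at CrCl ≤ 30, and a reader who infers such a requirement goes too far. It does not close the gap. These safeguards are discretionary and none mentions CrCl. The protocol did not leave CrCl 31 to 50 to judgment, and for Child-Pugh C it stated the conclusion that 7.2.7 leaves unsaid.

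Three other stronger readings also fail.
- A reader might infer that nothing tells the site to hold drug when creatinine rises on treatment. But the 7.2 table sets interruption rules by grade for non-hematologic toxicity attributable to olaparib, 6.3 requires interruption for treatment-related grade 3 or 4 events, and 8.1 lists increased creatinine in 3% to 45%. These rules cover some rises. They are not keyed to CrCl, and grade 1 brings no dose adjustment, so a small rise in a frail patient may trigger nothing.
- A reader might infer that renal function is unknown when olaparib starts, because surveillance visits carry no chemistry. Cycle 1 day 1 chemistry, or a sample within the preceding 7 days, is already required. The value will be there; the instruction is missing.
- A reader might infer that women at CrCl 31 to 50 start on 300 mg. Section 7.2.7 gives them 200 mg twice daily.

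**Conclusion.** The gap is real and should be fixed, within limits. A woman can satisfy the written renal criterion, be at CrCl ≤ 30 when olaparib is due, and have only the unreduced dose on paper, although the protocol reduces the dose for better renal function than hers. For patients already on olaparib the gap is partial.

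The size rests on Cockcroft-Gault with actual weight; another formula would shift the boundaries. How many patients would be affected cannot be derived: the documents give no distribution of age, weight or creatinine, and 8.1 does not say how large the creatinine rises are. The number is probably small, because creatinine near the limit must coincide with older age and low weight. The case for changing the text is the unprotected exposure and the ease of the repair, not frequency.

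**What to change.** State in 7.2.7 that olaparib is not started, or is withheld, at CrCl ≤ 30 mL/min. Name one formula (for example Cockcroft-Gault), the weight to use and rounding to whole mL/min, since the bands leave values between 30 and 31 unassigned. Calculate CrCl from the weight and chemistry already required at cycle 1 day 1 (or within 7 days before) and on day 1 of each later cycle.

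A CrCl floor in 3.1.7 and the synopsis is optional. Because drug starts only when CA125 doubles, an enrollment floor could exclude women whose renal function at that later time is not yet known; the check at drug start is the one that matters. A line in 6.1 saying that 7.2.7 also sets the starting dose at CrCl 31 to 50 would be a helpful clarification.

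The cost is a short amendment with no new test. A few enrolled patients may not start olaparib, or may have to hold it.

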7.2.8. Hepatic Impairment

Child-Pugh classification A or B: No dose adjustment.

Child-Pugh classification C: Use not recommended for use as safety and pharmacokinetics have not been studied in these patients.

8. ADVERSE EVENTS: LIST AND REPORTING REQUIREMENTS

Adverse event (AE) monitoring and reporting is a routine part of every clinical trial. For this trial, routine and expedited reporting will begin at the start of study therapy. The following list of AEs (Section 7.1) and the characteristics of an observed AE (Section 7.2) will determine whether the event requires expedited reporting **in addition** to routine reporting.

8.1. Adverse Events and Potential Risks List for Olaparib

>10%:

Cardiovascular: peripheral edema (14%)

Central nervous system: fatigue (≤67%), headache (15% to 26%), dizziness (7% to 20%)

Endocrine & metabolic: hypomagnesemia (5% to 14%)

Gastrointestinal: nausea (58% to 77%), abdominal pain (45%), vomiting (30% to 43%), diarrhea (21% to 37%), constipation (16% to 28%), dysgeusia (9% to 27%), dyspepsia (8% to 25%), decreased appetite (16% to 22%), stomatitis (4% to 20%; grades 3/4: 1%)

Genitourinary: urinary tract infection (13% to 14%)

Hematologic & oncologic: increased MCV (57% to 89%), decrease in absolute neutrophil count (25% to 51%; grades 3/4: 7% to 11%), anemia (23% to 44%; grades 3/4: 7% to 21%), neutropenia (5% to 27%; grades 3/4: 6% to 9%), leukopenia (2% to 25%; grades 3/4: 3% to 5%), thrombocytopenia (4% to 14%; grades 3/4: 1%)

Infection: influenza ($\leq 36\%$)

Neuromuscular & skeletal: asthenia ($\leq 66\%$), arthralgia ($\leq 30\%$), myalgia ($\leq 30\%$), musculoskeletal pain ($\leq 21\%$), back pain (14%)

Renal: increased serum creatinine (3% to 45%)

Respiratory: nasopharyngitis (\leq 36%), respiratory tract infection (\leq 36%), rhinitis (\leq 36%), sinusitis (\leq 36%), bronchitis (\leq 28%), cough (16% to 18%), dyspnea (13% to 15%)

1% to 10%:

Cardiovascular: edema (8% to 9%), pulmonary embolism (\leq 1%), venous thrombosis (\leq 1%)

Central nervous system: peripheral neuropathy (5%), depression, insomnia

Dermatologic: skin rash (5% to 6%), dermatitis (1%)

Gastrointestinal: upper abdominal pain (7%)

Hematologic & oncologic: lymphocytopenia (1% to 8%), myelodysplastic syndrome (acute myeloid leukemia; 1%)

Hypersensitivity: hypersensitivity reaction (2%)

Miscellaneous: fever (8% to 10%)

<1%, postmarketing, and/or case reports: pneumonitis

8.2 Adverse Event Characteristics

- **CTCAE term (AE description) and grade:** The descriptions and grading scales found in the revised NCI Common Terminology Criteria for Adverse Events (CTCAE) version 5.0 will be utilized for AE reporting. All appropriate treatment areas should have access to a copy of the CTCAE version 5.0.
- **Attribution** of the AE:
 - Definite The AE *is clearly related* to the study treatment.
 - Probable The AE *is likely related* to the study treatment.
 - Possible The AE *may be related* to the study treatment.
 - Unlikely The AE *is doubtfully related* to the study treatment.
 - Unrelated The AE *is clearly NOT related* to the study treatment.

8.3 Expedited Adverse Event Reporting

8.3.1 Expedited Reporting Guidelines

Use the protocol number and the protocol-specific patient ID assigned during trial registration on all reports.

Note: A death on study requires both routine and expedited reporting, regardless of causality. Attribution to treatment or other cause must be provided.

Death due to progressive disease should be reported as Grade 5 "Disease progression" in the system organ class (SOC) "General disorders and administration site conditions." Evidence that the death was a manifestation of underlying disease (e.g., radiological changes suggesting tumor growth or progression: clinical deterioration associated with a disease process) should be submitted.

FDA REPORTING REQUIREMENTS FOR SERIOUS ADVERSE EVENTS (21 CFR Part 312)

NOTE: Investigators MUST immediately report to the sponsor (NCI) ANY Serious Adverse Events, whether or not they are considered related to the investigational agent(s)/intervention (21 CFR 312.64)

An adverse event is considered serious if it results in ANY of the following outcomes:

- 1) Death
- 2) A life-threatening adverse event
- An adverse event that results in inpatient hospitalization or prolongation of existing hospitalization for ≥ 24 hours
- 4) A persistent or significant incapacity or substantial disruption of the ability to conduct normal life functions
- 5) A congenital anomaly/birth defect.
- 6) Important Medical Events (IME) that may not result in death, be life threatening, or require hospitalization may be considered serious when, based upon medical judgment, they may jeopardize the patient or subject and may require medical or surgical intervention to prevent one of the outcomes listed in this definition. (FDA, 21 CFR 312.32; ICH E2A and ICH E6).

ALL SERIOUS adverse events that meet the above criteria MUST be immediately reported within the timeframes detailed in the table below.

Hospitalization Grade 1 and Grade 2 Timeframes		Grade 3-5 Timeframes
Resulting in Hospitalization ≥ 24 hrs	10 Calendar Days	24-Hour 5 Calendar
Not resulting in Hospitalization \geq 24 hrs	Not required	Days

Expedited AE reporting timelines are defined as:

- "24-Hour; 5 Calendar Days" The AE must initially be submitted within 24 hours of learning of the AE, followed by a complete expedited report within 5 calendar days of the initial 24-hour report.
- "10 Calendar Days" A complete expedited report on the AE must be submitted electronically within 10 calendar days of learning of the AE.

Serious adverse events that occur more than 30 days after the last administration of investigational agent/intervention and have an attribution of possible, probable, or definite require reporting as follows: **Expedited 24-hour notification followed by complete report within 5 calendar days for:**

• All Grade 3, 4, and Grade 5 AEs

Expedited 10 calendar day reports for:

Grade 2 AEs resulting in hospitalization or prolongation of hospitalization

